### **10.1.3 Confidentiality**

All information generated in this trial will be considered confidential and will not be disclosed to anyone not directly concerned with the trial without the sponsor's prior written permission. Subject confidentiality requirements of the region(s) where the trial is conducted will be met. However, authorized regulatory officials and sponsor personnel (or their representatives) may be allowed full access to inspect and copy the records, consistent with local requirements. All IMPs, subject bodily fluids, and/or other materials collected shall be used solely in accordance with this protocol, unless otherwise agreed to in writing by the sponsor.

Subjects will be identified only by unique subject ID in the eCRF. If further subject identification is required, subjects' full names may be made known to a regulatory agency or other authorized officials if necessary, subject to local regulations.

### **10.1.4 Quality Control and Quality Assurance**

The sponsor will perform quality management activities for this trial in accordance with the ICH GCP guidance and standard operating procedures.

#### **10.1.4.1 Monitoring**

The sponsor has ethical, legal, and scientific obligations to follow this trial in accordance with established research principles, the applicable ICH GCP guidance, and applicable regulatory requirements and local laws. As part of a concerted effort to fulfill these obligations (maintain current personal knowledge of the progress of the trial), the sponsor's monitors will visit the site during the trial, as well as communicate frequently via telephone, e-mail, and written communications. In addition, all investigators/subinvestigators and trial site personnel will undergo initial and ongoing training for this particular trial, and this training will be clearly documented.

#### **10.1.4.2 Auditing**

The sponsor's Quality Assurance Unit (or representative) may conduct trial site audits. Audits will include, but are not limited to, IMP supply, presence of required documents, the informed consent process, site operations, delegation of authority and training, and a review of the eCRF with source documents, as applicable. The investigator will agree to cooperate and participate with audits.

Regulatory authorities may inspect the trial site during or after the trial. The investigator will cooperate with such inspections and will contact the sponsor immediately if such an inspection occurs.

### **10.1.5 Protocol Deviations**

In the event of a significant deviation from the protocol due to an emergency, accident, or mistake (eg, violation of informed consent process, IMP dispensing or subject dosing error, subject enrolled in violation of eligibility criteria or concomitant medication criteria), the investigator/subinvestigator or designee will contact the sponsor at the earliest possible time by telephone or via e-mail. The investigator/subinvestigator and sponsor (or designee) will come as quickly as possible to a joint decision regarding the subject's continuation in the trial. This decision will be documented by the investigator/subinvestigator and the sponsor (or designee) and reviewed by the site monitor.

Any major protocol deviation will be recorded in the eCRF along with the start date and details of the deviation.

### **10.1.6 Records Management**

#### **10.1.6.1 Source Documents**

Source documents are defined as the results of original observations and activities of a clinical investigation. Source documents will include but are not limited to medical records, electronic data, logs, and recorded data from automated instruments or applications. All source documents pertaining to this trial (excluding FBR documents) will be maintained by the trial sites and made available for direct inspection by authorized persons.

Investigators/trial sites will permit trial-related monitoring, audits, IRB review, and regulatory inspection(s) by providing direct access to source data/documents by authorized persons as defined in the ICF. In all cases, subject confidentiality must be maintained in accordance with local regulatory requirements.

#### **10.1.6.2 Data Collection**

During each subject's visit to the site, an investigator/subinvestigator or their designee participating in the trial will record information to document all significant observations. At a minimum, these notes will contain:

- Documentation of the informed consent process, including any revised consents;
- Documentation of the investigator/subinvestigator's decision to enroll the subject into the trial, the review of all inclusion/exclusion criteria prior to IMP administration, and confirmation of the subject's actual participation in the trial;
- The date of the visit and the corresponding Visit or Day in the trial schedule;
- General subject status remarks, including any significant medical findings. The severity, frequency, duration, action taken, and outcome of any AEs and the investigator/subinvestigator's assessment of relationship to IMP must also be recorded;
- Any changes in concomitant medications or dosages;
- A general reference to the procedures completed, including dosing and IMP compliance;
- The signature (or initials) and date of the investigator/subinvestigator (or designee) who made an entry in the medical record.

In addition, any contact with the subject via telephone or other means that provides significant clinical information will also be documented in the progress notes as described above.

Information from medical records and other source documents will be entered by investigative site personnel onto eCRFs in the sponsor's electronic data capture (EDC) system that is 21 CFR Part 11 compliant. Changes to the data will be captured by an automatic audit trail in the EDC system.

Electronic data not entered on eCRF, such as data received from central laboratories, will be reconciled using key data fields by the sponsor or designee with the eCRF data to ensure consistency.

#### **10.1.6.3 File Management at the Trial Site**

The head of the trial site will ensure that the trial site file is maintained in accordance with applicable ICH guidance and as required by applicable local regulations. The trial site will take measures to prevent accidental or premature destruction of these documents.

#### **10.1.6.4 Records Retention at the Trial Site**

The trial site will retain all documents and records related to this trial for the longest of the following 3 periods. However, if the sponsor requires a longer storage period, the storage period and method will be discussed with the sponsor.

- A period of at least 2 years after the date on which approval to market the IMP is obtained; However, in the case that development is discontinued or a notification to inform that the trial results will not be attached to the approval application is received, a period of at least 3 years after the decision date of stopping development, or the receiving date of the notification informing that the trial results will not be attached to the approval application.
- A period of at least 3 years after date of trial discontinuation/completion; OR
- The period of FBR sample storage.

The trial site must not dispose of any records relevant to this trial without either (1) written permission from the sponsor or (2) provision of an opportunity for the sponsor to collect such records. The trial site will be responsible for maintaining adequate and accurate electronic or hard copy source documents of all observations and data generated during this trial including any data clarification forms received from the sponsor. Such documentation is subject to inspection by the sponsor and relevant regulatory authorities.

#### **10.1.6.5 Publication Authorship Requirements**

Authorship for any Otsuka-sponsored publications resulting from the conduct of this trial will be based on International Committee of Medical Journal Editors (ICMJE) authorship criteria (<http://www.icmje.org/recommendations>). According to ICMJE guidelines, one may be considered an author only if the following criteria are met:

- 1) Substantial contributions to the conception or design of the work; or the acquisition, analysis, or interpretation of data for the work; AND
- 2) Drafting the work or revising it critically for important intellectual content; AND
- 3) Final approval of the version to be published; AND
- 4) Agreement to be accountable for all aspects of the work in ensuring that questions related to the accuracy or integrity of any part of the work are appropriately investigated and resolved.

All authors must meet the above criteria, and all who qualify for authorship based on the above criteria should be listed as authors.

Investigators or other trial subjects who do not qualify for authorship may be acknowledged in publications resulting from the trial. By agreeing to participate in the

Protocol 346-102-00003

trial, investigators or other trial subjects consent to such acknowledgement in any publications resulting from its conduct.

## 10.2 Appendix 2: Clinical Laboratory Tests

The tests detailed in Table 10.2-1 will be performed.

Table 10.2-1 Clinical Laboratory Assessments	
Hematology: Red blood cell count Hemoglobin Hematocrit Mean corpuscular hemoglobin concentration Mean corpuscular volume White blood cell (WBC) count WBC count with differential (neutrophils, eosinophils, basophils, monocytes, and lymphocytes) Platelets  Urinalysis (parameters other than pH and specific gravity will be included in the qualitative urinalysis) pH Protein Glucose Occult blood Bilirubin Urobilinogen Specific gravity Ketones	Serum Chemistry: Alkaline phosphatase ALT AST Total bilirubin Gamma glutamyl transferase Total protein Albumin Lactate dehydrogenase Blood urea nitrogen Creatinine Uric acid CK Serum electrolytes (sodium, potassium, chloride, calcium, bicarbonate) Glucose*

\*Testing will be performed in the fasting state.

### **10.3 Appendix 3: Contraceptive Guidance and Collection of Pregnancy Information**

Females of childbearing potential (FOCBP) are females whose menstruation has started and who are not documented as sterile (eg, have had a bilateral oophorectomy, or hysterectomy, or who have been postmenopausal for at least 12 months). Females of nonchildbearing potential do not meet definition of FOCBP.

For males and FOCBP, or their partners, who are sexually active, there must be a documented agreement that the subject and their partner will take effective measures (ie, 2 different approved methods of birth control or remains abstinent) to prevent pregnancy during the course of the trial and for 30 days after the last dose of IMP. Unless the subject or his/her partner is sterile (ie, females who have had a bilateral oophorectomy, have had a hysterectomy, or have been postmenopausal for at least 12 consecutive months; or males who have had a bilateral orchiectomy) or remains abstinent during the trial and for 30 days after the last dose of IMP, 2 of the following approved methods of birth control must be used: (vasectomy, tubal ligation, intrauterine device, birth control pill, or condom [all methods are approved or certificated in Japan]). Any single method of birth control, including vasectomy and tubal ligation, may fail, leading to pregnancy. Male subjects must agree not to donate sperm from the time of screening through the trial and until 30 days after the last dose of IMP.

Before enrolling males and females in this clinical trial, investigators or subinvestigators must review the below information about trial participation as part of the ICF process.

The topics should generally include:

- General information
- The informed consent form
- Pregnancy prevention information
- Contraceptives in current use
- Follow-up of a reported pregnancy

Before trial enrollment, males and FOCBP must be advised of the importance of avoiding pregnancy during trial participation and the potential risk factors for an unintentional pregnancy. Subjects must sign the ICF confirming that the above-mentioned risk factors and the consequences were discussed.

A urine pregnancy test will be performed on all FOCBP. If a urine test is performed and is positive, the investigator or subinvestigator will follow-up with a confirmatory serum test (for human chorionic gonadotropin) (except at screening).

During the trial, all FOCBP should be instructed to contact the investigator or subinvestigator immediately if they suspect they might be pregnant (eg, missed or late menstrual cycle). Male subjects must be instructed to contact the investigator immediately, during the trial, if their partner suspects that they might be pregnant (eg, missed or late menstrual cycle).

If a subject is suspected to be pregnant before she receives IMP, the IMP administration must be withheld until the results of serum pregnancy tests are available. If the pregnancy is confirmed, the subject must not receive the IMP and must not be enrolled in the trial. If pregnancy is suspected while the subject is taking IMP, the IMP must be withheld immediately (if reasonable, taking into consideration any potential withdrawal risks) until the result of the pregnancy test is known. If pregnancy is confirmed, the IMP will be permanently discontinued in an appropriate manner (eg, dose tapering if necessary for subject safety) and the subject will be withdrawn from the trial. Exceptions to trial discontinuation may be considered for life-threatening conditions only after consultations with the IRE contact (see the title page of this protocol for contact information).

The investigator or subinvestigator must immediately notify the sponsor (within 24 hours) of any pregnancy associated with IMP exposure during the trial and for at least 30 days after the last dose of IMP, and record the event on the IRE form or other documentation and forward it to the sponsor. The sponsor will forward the Pregnancy Surveillance Form(s) to the investigator or subinvestigator for monitoring the outcome of the pregnancy.

Protocol required procedures for trial discontinuation and follow-up must be performed on the subject unless contraindicated by pregnancy (eg, x-ray studies). Other appropriate pregnancy follow-up procedures should be considered if indicated. In addition, the investigator or subinvestigator must report to the sponsor, on the Pregnancy Surveillance Form(s), follow-up information regarding the course of the pregnancy, including perinatal and neonatal outcome. Infants will be followed for a minimum of 6 months from the date of birth.

## **10.4 Appendix 4: Protocol Amendments**

The investigator or subinvestigator will not make any changes to this protocol without the sponsor's prior written consent and subsequent approval by the IRB. Any permanent change to the protocol, whether an overall change or a change for specific trial site(s), must be handled as a protocol amendment. Any amendment will be written by the sponsor. Each amendment will be submitted to the IRB, as required by local regulations. Except for "administrative" or "nonsubstantial" amendments, investigators or subinvestigator will wait for IRB approval of the amended protocol before implementing the change(s). Administrative amendments are defined as having no effect on the safety of subjects, conduct or management of the trial, trial design, or the quality or safety of IMPs used in the trial. A protocol change intended to eliminate an apparent immediate hazard to subjects should be implemented immediately, followed by IRB notification within local applicable timelines. If required, the sponsor will submit protocol amendments to the applicable regulatory agencies within local applicable timelines.

When the IRB, investigators, and/or the sponsor conclude that the protocol amendment substantially alters the trial design and/or increases the potential risk to the subject, the currently approved written ICF will require similar modification. In such cases, after approval of the new ICF by the IRB, repeat written informed consent will be obtained from subjects enrolled in the trial before expecting continued participation and before the amendment-specified changes in the trial are implemented.

### **10.4.1 Protocol Amendment(s)/Administrative Change(s)**

Not applicable.

Appendix 4	Preferred Terms for Statins and Ezetimibe.....	22
Appendix 5	Classification of Adverse Events of Special Interest.....	23
Appendix 6	Statin Intensity and Type	25
Appendix 7	Criteria for Hy's Law.....	28
Appendix 8	List of Figures and Tables	29
Appendix 9	List of Subject Data Listings	39

List of Abbreviations and Definition of Terms

Abbreviation	Definition
AE	adverse event
ALP	alkaline phosphatase
ALT	alanine aminotransferase
apo B	apolipoprotein B
AST	aspartate aminotransferase
BMI	body mass index
CRF	case report form
ECG	electrocardiogram
eGFR	estimated glomerular filtration rate
HbA1c	glycosylated hemoglobin
HDL-C	high-density lipoprotein-cholesterol
hsCRP	high-sensitivity C-reactive protein
ICH	International Council for Harmonisation of Technical Requirements for Pharmaceuticals for Human Use
IMP	investigational medicinal product
LDL	low-density lipoprotein
LDL-C	low-density lipoprotein cholesterol
MedDRA	Medical Dictionary for Regulatory Activities
non-HDL-C	non-high-density lipoprotein-cholesterol
PT	preferred term
OC	observed cases
QTc	corrected QT interval
QTcF	QT interval corrected for heart rate using Fridericia's formula
SAE	serious adverse event
SAP	statistical analysis plan
SOC	system organ class
TC	total cholesterol
TEAE	treatment-emergent adverse event
TG	triglyceride
ULN	upper limit of normal
WHODD	World Health Organization Drug Dictionary

1 Introduction

This statistical analysis plan (SAP) documents the detailed methods of the statistical analysis planned in Trial 346-102-00003. In this clinical trial, data will be summarized at the interim and final time points when observation for at least 24 weeks (or up to discontinuation) has been completed in all subjects. The interim data cutoff date will be 18 Mar 2024.

2 Trial Objectives

Primary:

- To assess the safety of ETC-1002 at 180 mg administered for 52 weeks in patients with hyper-low-density lipoprotein (LDL) cholesterolemia

Secondary:

- To assess the effects of ETC-1002 at 180 mg administered for 52 weeks on LDL-C in patients with hyper-LDL cholesterolemia
- To assess the effects of ETC-1002 on non-high-density lipoprotein-cholesterol (non-HDL-C), total cholesterol (TC), apolipoprotein B (apo B), high-sensitivity C-reactive protein (hsCRP), and glycosylated hemoglobin (HbA1c)

3 Trial Design

3.1 Type/Design of Trial

The trial population will include patients with an inadequate response to statins who cannot achieve the lipid management goals despite statin therapy, and patients who are determined to have difficulty in treatment with statins and cannot achieve the lipid management goals. Patients with difficulty in treatment with statins are defined as those who cannot achieve the lipid management goals for the following reasons: patients who have experienced safety problems caused by statin administration which resolved after discontinuation or dose reduction, or patients who have a history of statin administration and are judged to have concerns of safety problems associated with the administration or dose increase of statins. In addition, subjects who have completed the treatment period in the phase 3 confirmatory trial (Protocol No. 346-102-00002) can also be enrolled in this trial, as they are in the same population and their enrollment allows assessments of the occurrence of adverse events (AEs) over a longer period.

A schematic of the trial design is presented in [Figure 3.1-1](#).

This trial consists of the screening period, the treatment period, and the follow-up period.

Subjects who are judged to be eligible at screening will proceed to the treatment period.

Subjects proceeding to the treatment period who have been receiving treatment using lipid-lowering drugs since before informed consent should continue the treatment without changing the type or dose and regimen in addition to being orally administered ETC-1002 at 180 mg once daily for 52 weeks.

[figure not shown]

Figure 3.1-1 Trial Design Schematic

3.2 Trial Treatments

Subjects who proceed to the treatment period will orally receive ETC-1002 180-mg tablets once daily for 52 weeks. Administration of lipid-lowering drugs used before informed consent should be continued without changing the type or dose and regimen.

3.3 Trial Population

This is a multicenter, open-label, uncontrolled, long-term trial to assess the safety and efficacy of ETC-1002 long term administration in patients with hyper-LDL cholesterolemia, who are receiving treatment for hyper-LDL cholesterolemia but have inadequate control and cannot achieve the lipid management goals. The trial population will include patients with an inadequate response to statins who cannot achieve the lipid management goals despite statin therapy, and patients who are determined to have difficulty in treatment with statins due to the occurrence of or potential for safety problems and cannot achieve the lipid management goals. In addition, subjects who have completed the treatment period in the phase 3 confirmatory trial (Protocol No. 346-102-

00002) can also be enrolled in this trial, as they are in the same population and their enrollment allows assessments of the occurrence of AEs over a longer period.

3.4 Trial Visit Window

For the efficacy and safety endpoints (except for AEs), acceptable windows of analysis visits will be set, and the analysis will be based on the analysis visits, regardless of the time points recorded in the case report form (CRF). Analysis visits will be specified based solely on fasting data for non-HDL-C, TC, HDL-C, TG, and LDL-C (calculated using the Friedewald formula) among the fasting lipid parameters for the efficacy endpoints. The handling of fasting data is described in [Section 5.3](#).

Acceptable windows of analysis visits are shown in [Table 3.4-1](#). The start day of investigational medicinal product (IMP) administration is defined as Day 1. Baseline is defined as the last data before the start of IMP administration. If multiple data points are available for a certain acceptable window, the last data point will be used for the analysis. Data collected more than 2 days after the last IMP administration will be excluded. The last data obtained between the initial IMP administration and 2 days after the last IMP administration will be defined as the Last Visit.

Table 3.4-1 Acceptable Windows of Analysis Visits	
Week	Trial Day Interval
Baseline	- 1
Week 4	2 - 43
Week 8	44 - 71
Week 12	72 - 99
Week 16	100 - 127
Week 20	128 - 155
Week 24	156 - 183
Week 28	184 - 211
Week 32	212 - 239
Week 36	240 - 267
Week 40	268 - 295
Week 44	296 - 323
Week 48	324 - 351
Week 52	352 - 375
Last Visit	Last data obtained between the initial IMP administration and 2 days after the last IMP administration in the treatment period
Week 56 (FU)	Time point recorded in the CRF

4 Sample Size

Assuming a withdrawal of approximately 20 subjects during the treatment period, the target number of subjects is set at 120 to ensure that 100 subjects will complete the 1-year treatment to assess the safety of ETC-1002 at 180 mg in long-term administration.

5 Statistical Analysis Datasets

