Clinical Laboratory Test Value Changes: It is the investigator/subinvestigator's responsibility to review the results of laboratory tests for each individual subject as they become available. This review will be documented by the investigator/subinvestigator's dated signature on the laboratory report. The investigator or subinvestigator may repeat the laboratory test or request additional tests to confirm the results of the original laboratory tests. If this laboratory test value is considered medically relevant (ie, clinically significant) by the investigator or subinvestigator (subject is symptomatic, requiring corrective treatment or further evaluation), or if the laboratory test value leads to discontinuation, and/or fulfills a seriousness criterion, this is considered an AE. However, if an abnormal result is found in a test performed at the central laboratory and is considered an AE, the course should be confirmed with the test results of the central laboratory in principle.

Severity: Adverse events will be graded on a 3-point scale below:

- |                      |  |
|----------------------|--|
| 1 = Mild:     | Discomfort noticed, but no disruption to daily activity.         |
| 2 = Moderate: | Discomfort sufficient to reduce or affect normal daily activity. |
| 3 = Severe:   | Inability to work or perform normal daily activity.              |

**IMP Causality:** Assessment of causal relationship of an AE to the use of the IMP is defined as follows:

- Related:** There is a reasonable possibility of a temporal and causal relationship between the IMP and the AE.
- Not Related:** There is no temporal or causal relationship between the IMP and the AE.

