9.3 Clinical Laboratory Data

Among the urinalysis parameters in laboratory tests, those other than pH and specific gravity will be included in the qualitative urinalysis.

For parameters other than the qualitative urinalysis, descriptive statistics of the actual value and change from baseline will be calculated at each time point. For qualitative urinalysis parameters, shift tables at each time point from baseline will be prepared. For parameters other than qualitative urinalysis, measured values will be categorized using

the reference range to “below the lower limit of reference range,” “within the reference range,” and “above the upper limit of reference range,” and shift tables at each time point from baseline will be prepared.

The number and percentage of subjects meeting the criteria for identifying laboratory values of potential clinical relevance ([Appendix 2: Criteria for Identifying Laboratory Values of Potential Clinical Relevance](#)) and Hy’s law ([Appendix 7: Criteria for Hy’s Law](#)) after IMP administration will be calculated. All data obtained after IMP administration during the treatment period will be analyzed, including those obtained at unscheduled visits.

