9.6 Electrocardiogram Data

For ECG parameters (heart rate, PR interval, RR interval, QRS interval, QT interval, and QTcF), descriptive statistics of the actual value and change from baseline will be calculated at each visit (Weeks 12, 24, 36, and 52).

The number and percentage of subjects with an actual value of QTcF of >450 ms, >480 ms, or >500 ms at any postdose time point will be calculated. In addition, the number and percentage of subjects with a change from baseline in QTcF of >30 ms or >60 ms at any postdose time point will be calculated. All data obtained after IMP administration will be analyzed, including those obtained at unscheduled visits. Similarly, the number and percentage of subjects meeting these criteria at each postdose time point will also be calculated.

For assessment of normality/abnormality, shift tables at baseline and each time point will be prepared.

The number and percentage of subjects meeting the criteria for identifying ECG measurements of potential clinical relevance ([Appendix 3: Criteria for Identifying ECG Measurements of Potential Clinical Relevance](#)) after IMP administration will be calculated. All data obtained after IMP administration will be analyzed, including those obtained at unscheduled visits.

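### The last-value-in-window rule lets a confirmatory repeat replace an abnormal scheduled laboratory result in the Week 4 to 48 by-visit and shift tables

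*SAP*

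**What the plan says.** SAP 3.4 sets the scope: "For the efficacy and safety endpoints (except for AEs), acceptable windows of analysis visits will be set". Values are placed by trial day, whatever visit label the CRF carries. Where a window holds several values, "If multiple data points are available for a certain acceptable window, the last data point will be used for the analysis". No preference is given to the scheduled, nearest or worst value. Values taken more than 2 days after the last dose are excluded.

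SAP 9.3 then calculates laboratory descriptive statistics by time point and classifies values as below, within or above the reference range; "shift tables at each time point from baseline will be prepared". Only the potential-clinical-relevance and Hy's law counts in that section are stated to use all post-dose treatment-period data, unscheduled visits included.

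Protocol 8.8.1 provides for repeats: "The investigator or subinvestigator may repeat the laboratory test or request additional tests to confirm the results of the original laboratory tests". Where an abnormal central result is judged an AE, "the course should be confirmed with the test results of the central laboratory in principle". Protocol 8.7.1 has the central laboratory send its results to the sponsor electronically.

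**The concern.** A confirmatory repeat is ordered because the first value was abnormal, and it always comes later. Under a last-value rule it takes the scheduled value's place whenever both fall in one window. Such a repeat can leave the tabulated category abnormal or move it to normal. It cannot add an abnormal result that was not already there.

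Safety is the primary objective, and the trial has no control arm whose tables would carry the same effect for comparison. Protocol 8.7.1 describes the AST, ALT, hemoglobin, creatinine and urea nitrogen changes seen outside Japan as not clinically significant. Modest movement across a reference limit is what by-visit and shift tables are there to show, and that is where a transient excursion can drop out.

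**Working it through.** The plan gives no figure for this effect, so there is none to reproduce. The check covers whether a repeat falls in the same window, which outputs are exposed, and what would determine the size.

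**1. Room for a repeat in the window.** Inputs: the windows in SAP Table 3.4-1, and the target days and ±7-day tolerance in the Protocol Schedule of Assessments. Target day = 7 × week + 1.

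| Week | Target day | Window end | Days left: on-time visit | Visit 7 days late | Visit 7 days early |
|---|---|---|---|---|---|
| 8 | 57 | 71 | 14 | 7 | 21 |
| 12 | 85 | 99 | 14 | 7 | 21 |
| 48 | 337 | 351 | 14 | 7 | 21 |
| 52 | 365 | 375 | 10 | 3 | 17 |

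All windows from Week 4 to Week 48 end 14 days after the target. With visit offset k (−7 to +7) and repeat lag L, the repeat stays in the window when k + L ≤ 14:
- L ≤ 7: all 15 permitted visit days.
- L = 10: k ≤ 4, so 12 of 15.
- L = 14: k ≤ 0, so 8 of 15.

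Example: ALT above the ULN but below 3 × ULN on Day 85, retested in range on Day 92. Since 92 ≤ 99, Week 12 is tabulated as within the reference range.

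**2. Week 52 and discontinuation.** The Week 52 window leaves 10 days after an on-time visit, but the 2-day cut excludes most repeats made after treatment ends. The Discontinuation Visit is itself planned within 2 days of the last dose. Replacement there is possible only in a narrow interval.

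**3. Which laboratory outputs are exposed.**

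| Output | Values used | Exposed? |
|---|---|---|
| Descriptive statistics by visit (SAP 9.3) | Last in window | Yes |
| Reference-range shift tables (SAP 9.3) | Last in window | Yes |
| Potential clinical relevance, Hy's law (SAP 9.3) | All post-dose, unscheduled included | No |
| AE and AESI tables (SAP 9.2) | AEs exempt from windows | No |
| Abnormal-value and laboratory listings (SAP Appendices 8 and 9) | Individual values | No |

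**4. What is left uncovered.** Appendix 2 limits lie well above the reference limits for several key analytes: AST and ALT at 3 × ULN, CK at 4 × ULN. Excursions between the two limits that are not reported as AEs are summarised only in the exposed tables. The same holds for non-AE changes in analytes that Protocol Table 10.2-1 collects but Appendix 2 omits, such as gamma glutamyl transferase and lactate dehydrogenase.

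**5. Size and direction.** Let P be the abnormal share at the scheduled test, r the share of those repeated in the same window with the result in the analysed data, and q the share of such repeats that are normal. Let s be the share of normal scheduled values followed by a later test in the window, and a the share of those later tests that are abnormal. Then

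tabulated abnormal share = P × (1 − r × q) + (1 − P) × s × a.

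The net change is toward normal only if P × r × q exceeds (1 − P) × s × a. The documents give none of r, q, s or a.

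**The case against.** The strongest reply is that little is lost. A value judged clinically significant becomes an AE under Protocol 8.8.1. SAP Appendix 5 has AESI terms for ALT, AST, CK, creatinine, uric acid and hemoglobin. The Appendix 2 counts use all data, and the listings keep the original values. This stands, and it confines the point to the residue in step 4.

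The sentence on following results at the central laboratory applies only to results already considered AEs. For milder abnormalities a repeat is optional, and the documents do not say it must go to the central laboratory. This also stands: r could be small.

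A reader might infer that the shift tables as a whole are biased toward normal. The documents do not support that. SAP 9.3 recognises unscheduled visits in general, and a test prompted by new symptoms can replace a normal value with an abnormal one. Protocol 1.3.1.2 allows re-testing in screening, and baseline is the last pre-dose value. A normalising retest there makes later abnormal values count as new shifts.

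A reader might also extend the point to ECGs or vital signs, since the window rule formally covers them. SAP 9.6 acknowledges unscheduled ECGs, but the protocol has no repeat-ECG provision like the laboratory one and its any-time QTcF counts use all data. No vital-sign repeat mechanism is shown either.

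The sponsor may say that unscheduled values were never meant to enter by-visit tables. SAP 3.4 does not say so. If that is the intention, one sentence would settle it.

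**Conclusion.** The point holds for laboratory by-visit statistics and reference-range shift tables at Weeks 4 to 48. A confirmatory repeat in the same window replaces the abnormal scheduled result, and a normal repeat removes the excursion from those tables. This assumes that the repeat reaches the analysed data and that unscheduled values are eligible for windows, as SAP 3.4 reads.

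The consequence is limited to mild excursions below Appendix 2 limits that are not reported as AEs, and to analytes with no Appendix 2 criterion. Marked abnormalities are not lost. A reader might want a percentage of shifts erased, but any such figure would come from an assumed repeat rate, so none is given. The fraction of abnormal scheduled results erased is r × q, which cannot exceed r, and r is unknown. The net direction is not fixed for every table. This is an inexpensive improvement to the primary-objective safety displays and does not invalidate the safety analysis.

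**What to change.** - **SAP 3.4:** for laboratory by-visit tables, use the value from the scheduled visit; if there is none, use the value nearest the target day.
- **SAP 9.3 and Appendix 8:** add a laboratory shift table from baseline to the worst on-treatment post-baseline value, unscheduled values included. Show shifts to low and shifts to high separately, because worst has no single meaning across below, within and above range.
- **Lipids:** leave as they are. SAP 3.4 and 5.3 already restrict non-HDL-C, TC, HDL-C, TG and Friedewald LDL-C to fasting values, and direct LDL-C is used irrespective of fasting.

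The cost is SAP wording and some programming, with no new data. Worst-value percentages rise with the number of tests per subject and will look less favourable, so the table should carry a note saying so and be read beside the by-visit tables.
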